### **13.2.3 Retention of records**

The Principal Investigator of The Case Comprehensive Cancer Center supervises the retention of all documentation of adverse events, records of study drug receipt and dispensation, and all IRB correspondence for as long as needed to comply with local, national and international regulations. No records will be destroyed until the Principal Investigator confirms destruction is permitted.

### **13.2.4 Audits and inspections**

Authorized representatives of the sponsor, a regulatory authority, an Independent Ethics Committee (IEC) or an Institutional Review Board (IRB) may visit the site to perform audits or inspections, including source data verification. The purpose of an audit or inspection is to systematically and independently examine all study-related activities and documents to determine whether these activities were conducted, and data were recorded, analysed, and accurately reported according to the protocol, Good Clinical Practice (GCP), guidelines of the International Conference on Harmonization (ICH), and any applicable regulatory requirements. For multi-center studies, participating sites must inform the sponsor-investigator of pending audits.

## **14.0 STATISTICAL CONSIDERATIONS**

### **14.1 Study Hypotheses**

The primary hypothesis is that the incidence of depression in patients with localized pancreatic and related cancer will be lower with treatment with escitalopram compared to placebo at 12 weeks.

## 14.2 Analysis Plans

The primary endpoint of the study is depression by QIDS at 12 weeks.

### Depression

The primary outcome is moderate or greater depression defined as a QIDS-SR score greater than 11. All patients will have localized disease, but be stratified by extent of disease: resectable vs. unresectable, based on imaging and as determined by the PI Based on the Tumor Profile Assessment. Under Generalized Linear Model (GLM) framework, a modified Poisson model can be constructed as the working model to directly estimate the relative risk of depression at each measurement time through 12 weeks (Zou and Donner 2013). Measurement time will be treated as a categorical/ordinal variable to allow for differing risk of depression in controls at each time point. The model will adjust for baseline QIDS-SR score as a continuous covariate and the stratification variable. Generalized Estimating Equation (GEE) will be used to account for correlation among the 6 repeated post-randomization measurements through month 3 for each participant. A time by randomization assignment interaction variable will be included to allow for estimation of the relative risk at each measurement time. The primary interest is to compare the two treatment groups at 12 weeks. This comparison will be performed at the one-sided alpha=0.10 level.

Since the GEE estimates are only valid under the Missing At Random (MAR) assumption if the working correlation structure is correctly specified, missing dichotomous outcomes will be imputed using Multiple Imputation (MI) prior to analysis (Li et al 2006). Estimates using this method are consistent under the MAR assumption (Beunckens et al 2008).

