### **1.2 Rationale for Proposed Study**

A recent randomized study of patients with head and neck cancer offers pioneering insights into the potential benefit of this approach. Lydiatt et al. randomized 148 patients with head and neck cancer of varying stages to escitalopram (Lexapro, an SSRI, 20 mg/day, except 10 mg/day during week 1) or placebo. Patients were included in the study if they were not depressed or had mild depression at the start of treatment, as indicated by a QIDS-SR score < 11. There were minimal adverse effects in both treatment groups. Depression was more common at later time points in the placebo group compared to the treatment group (24% vs. 10%), and the benefit persisted in a multivariable analysis. Thus, the number needed to treat to prevent a single case of depression was just 7 people. Additionally, there was better quality of life noted in patients in the treatment group at every time point in the study, and as early as after 1 month of treatment. Based on this study, we will administer the same dose of study drug. We will administer escitalopram at 10 mg/day for 2 weeks, 20 mg/day for 8 weeks, and 10 mg/day for the final 2 weeks (ramp up and ramp down periods) for a total of 12 weeks.

Due to the fact that depression is more common in pancreatic cancer than any other cancer type (40% of patients), depression symptoms overlap with presenting signs and symptoms of pancreatic cancer, and depression screening is currently not standard practice for patients undergoing treatment for pancreatic cancer, the QIDS survey (nor any other tool) has been validated in the

pancreatic cancer population, we will include all patients with localized pancreatic cancer in this trial, regardless of depression score. **Importantly, patients noted to have either severe depression per the QIDS screen or suicidal ideation will be referred to a study psychiatrist for a more thorough evaluation and care plan with consideration of starting a second pharmacologic agent. However, these patients will continue on study in a blinded fashion taking placebo or escitalopram.**

We will look at QIDS scores at 12 weeks as the primary study outcome. We hypothesize that patients receiving escitalopram will have a lower rate of moderate (or worse) depression, compared to patients receiving placebo.

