#### QIDS (Quick inventory of depressive symptomatology)

QIDS is a 16-item survey that addresses each of the nine symptom domains covered in the DSM-V criteria for Major depressive disorder (depressed mood, loss of interest or pleasure, concentration/decision making, self-outlook, suicidal ideation, energy/fatigability, sleep, weight/appetite change, and psychomotor changes). The tool is used both for depression screening, and to measure depression severity, and has been heavily validated against established surveys. Its effectiveness is proven. The tool is straight forward, and is administered in either a self-reported form (SR), or a clinician-rated (CR) form, and requires minimal training. The QIDS scores range from 0-27. Scores are interpreted as follows:

0-5	No depression
6-10	Mild depression
11-15	Moderate depression
16-20	Severe depression
21-27	Very severe depression

In this study, we will be using the QIDS to measure the rate of depression at each time point, with the incidence of worsening depression at 12 weeks as a primary outcome. Patients with a QIDS score  $\geq 16$  at any time point will be referred to a psychiatrist for a more thorough evaluation and consideration for additional therapy.

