#### **Primary:**

The primary outcome measure will be depression rates, based on answers from the QIDS form. Depression is reflected by a score  $\geq 11$  (moderate depression or worse).

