#### Unblinding Procedures:

- Patients will be unblinded if study drug is discontinued for the Adverse Events of Special Interest (hemorrhage, suicidal ideation and mania) as described in Table 7.1.
- Patients will be unblinded if study drug is discontinued due to Grade 4 hyponatremia as described in Table 7.1.

- Patients will be unblinded if they meet the criteria for removal from study as defined in Section 6.2.
- Patients will be unblinded at the time of their Day 85 (Week 13) end of treatment visit.

Patients will be unblinded by IDS staff as outlined in the Unblinding Manual. Patients who are unblinded before they complete all study visits will be asked to continue to have study-related phone calls with study staff and complete all study-related questionnaires. Patients who are unblinded prior to the end of treatment visit and undergo tumor resection will be required to have the research tissue sample and post-surgery research blood samples taken.

An assessment of depression will be made by the treating physician. Based on the assessment, patients who received escitalopram may be given the option of continuing the medication either under the supervision of their medical oncologist or primary care provider. If this occurs, the patient will obtain escitalopram from commercial supply at the dose prescribed by the patient's medical oncologist, primary care physician or other provider.

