## **12.0 MEASUREMENT OF EFFECT**

Efficacy will be defined as the prevention of incidents of moderate or greater depression defined as a QIDS-SR score greater than 11 at 12 weeks.

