## **14.3 Sample Size Considerations**

The primary objective of this study is to obtain preliminary evidence of efficacy of the treatment in preventing incident moderate or greater depression defined as a QIDS-SR score greater than 11 at 12 weeks. Assuming 23 subjects per arm and a true rate of depression in the control arm of 40%, we have 80% power to detect a difference if the true rate in treatment arm is 13.8% using a one-sided alpha of 0.10. Assuming an observed rate of 40% in the control arm, the upper limit of the 80% confidence interval for the risk ratio ranges from 0.56 when the observed treatment arm rate is 10% to 1.09 when the observed treatment arm rate is 25%. Any patient who has less than 65% compliance rate after four weeks of escitalopram/placebo (as determined during bi-weekly pill diary review) will be considered not evaluable and will be replaced. Any patient who experiences a serious adverse event that requires discontinuation of study drug within the first four weeks of treatment will be considered not evaluable and will be replaced.

To achieve a final sample size of 46 (23 per arm) at 12 weeks we will randomize 55 patients allowing for up to 15% attrition.

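### The primary event is QIDS ≥ 11 in Section 2.4 but above 11 in Sections 12.0, 14.2 and 14.3, so a score of exactly 11 is classified both ways

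*Combined protocol and SAP*

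**What the plan says.** Section 2.4 (Primary) counts a score of 11 as depression: "Depression is reflected by a score $\geq 11$ (moderate depression or worse").

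Three later sections use a strict inequality under the same severity label:

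- Section 14.2 (Depression), the primary analysis: "The primary outcome is moderate or greater depression defined as a QIDS-SR score greater than 11".
- Section 12.0, the efficacy definition: "moderate or greater depression defined as a QIDS-SR score greater than 11 at 12 weeks".
- Section 14.3, the sample size: "incident moderate or greater depression defined as a QIDS-SR score greater than 11 at 12 weeks".

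The QIDS description in Section 1.2 gives the scale and its bands ("The QIDS scores range from 0-27. Scores are interpreted as follows"): 6–10 is mild and 11–15 is moderate. Section 1.2 also describes the model trial in head and neck cancer as enrolling patients with no or mild depression, identified by a score below 11.

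All of this is current text and none of it comes from the summary of changes.

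**The concern.** The strict rule conflicts with the endpoint section, with the severity table, and with its own label, since moderate or greater includes 11 on the protocol's own bands. A programmer who follows Section 14.2 literally would code a moderately depressed patient scoring 11 as a non-event.

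This is the event definition of the only primary endpoint. Section 14.2 applies it at every post-randomization measurement in the GEE model and imputes missing values of the dichotomy, so the cut-off affects the model and the imputation as well as the 12-week counts.

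With two definitions on record, the choice could be made after results are known. Section 6.1 makes this more pressing: "Patients will be unblinded at the time of their Day 85 (Week 13) end of treatment visit". Arm and outcome therefore become known patient by patient.

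**Working it through.** **Inputs from the plan.** 23 per arm, control rate 40%, treated rate 13.8%, one-sided alpha 0.10, 80% power (Section 14.3). QIDS totals are whole numbers from 0 to 27 (Section 1.2).

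**1. The plan's own figure.** Exact binomial enumeration of the pooled two-proportion z-test, 23 per arm, 0.40 v 0.138, one-sided 0.10, gives power 80.1%. The unpooled normal approximation gives 79.3%. The stated 80% reproduces. The calculation takes the two rates as given, so it does not depend on the cut-off.

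**2. Where the rules differ.** For whole numbers, above 11 means 12 or more. The rules disagree only at a score of 11.

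**3. Weight of one patient.** 1/23 = 4.3 percentage points of that arm's rate.

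**4. Effect on the test.** The planned rates correspond to about 0.40 × 23 = 9.2 control events and 0.138 × 23 = 3.2 treated events. Recoding control patients who score 11, with z = (a/23 − b/23) / √[p̄(1 − p̄) × 2/23] and p̄ = (a + b)/46:

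| Events, control v treated | z | One-sided p, pooled z | One-sided p, log risk ratio |
|---|---|---|---|
| 9 v 3 | 2.01 | 0.022 | 0.033 |
| 8 v 3 | 1.73 | 0.042 | 0.054 |
| 7 v 3 | 1.43 | 0.076 | 0.087 |
| 6 v 3 | 1.12 | 0.132 | 0.140 |

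From 9 v 3, losing one or two control events leaves the result significant. From 7 v 3, losing one reverses it.

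**5. How often the rules would disagree.** This needs the share of controls scoring exactly 11, written s, which the documents do not give. It also needs the cut-off behind the 40%. The background statement that "depression is more common in pancreatic cancer than any other cancer type (40% of patients") names no QIDS threshold. I assume s = 2%, 5% or 10%, and a risk ratio of 0.138/0.40 = 0.345 for every score category, so the treated share is 0.345s. Each arm is then trinomial (12 or more, exactly 11, 10 or less). Disagreement is the exact probability that the pooled z-test is significant under one rule and not under the other.

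| s | Disagree, 40% means ≥ 11 | Disagree, 40% means > 11 |
|---|---|---|
| 2% | 5.0% | 4.6% |
| 5% | 10.5% | 8.6% |
| 10% | 18.6% | 12.3% |

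**6. Power if planning and analysis use different cut-offs** (exact pooled z, same assumptions):

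| s | 40% means ≥ 11, > 11 analysed | 40% means > 11, ≥ 11 analysed |
|---|---|---|
| 2% | 0.38 v 0.131: 77.9% | 0.42 v 0.145: 82.1% |
| 5% | 0.35 v 0.121: 74.2% | 0.45 v 0.155: 84.6% |
| 10% | 0.30 v 0.1035: 67.1% | 0.50 v 0.1725: 88.1% |

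**The case against.** The strongest reply is that the intended rule can be recovered. Every sentence with the strict inequality carries the label moderate or greater, the severity table starts that band at 11, and Section 2.4 says so outright. Only ≥ 11 satisfies all of these, so this looks like a repeated drafting slip and not two rival endpoints. Nor does anything in the plan suggest that a post hoc choice is intended. That is fair as to intent. It does not remove the problem, because the strict wording sits in the section the analysis will be coded from. Followed literally it gives one consistent rule, but one that misclassifies scores of 11.

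The sizes are also open to challenge. The 2–10% range is assumed. At 10%, with 40% meaning ≥ 11, a quarter of control events would sit on one of the 17 scores from 11 to 27. A constant risk ratio is a further assumption, since a drug that lowers scores could move treated patients down into the score-11 cell. The planned analysis is an adjusted GEE model with multiple imputation on all randomized patients (55 planned), not an unadjusted z-test on 46. With 28 v 27 patients, one patient is worth 3.6 to 3.7 points, and the same calculation gives disagreement of about 5%, 10% and 17%, or 4%, 8% and 11%. These points make the frequencies illustrative and slightly smaller. They do not touch the contradiction, which needs no assumption.

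**Conclusion.** The concern holds: the primary event definition is wrong as written in Sections 12.0, 14.2 and 14.3, and it must be corrected. The rest of the protocol supports ≥ 11.

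On size, the firm statements are that each patient scoring 11 is worth 4.3 points of an arm's rate at 23 per arm, and that one such control patient can reverse a result near the boundary. At the planned effect, recoding one or two controls changes nothing. The disagreement of roughly 5–19% of trials, and the power of 67–78% or 82–88% under mismatched cut-offs, depend on the assumed share scoring 11, a constant risk ratio and an unadjusted test. The sample size and the stated 80% power need no change if one cut-off applies throughout.

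**What to change.** - In Sections 12.0, 14.2 and 14.3, define the event as a QIDS-SR score of 11 or greater, matching Section 2.4 and the severity table.
- Add a sentence to Section 14.3 stating that the 40% and 13.8% rates refer to that cut-off.
- Optionally, name a cut-off of 12 or more as a sensitivity analysis.
- Make the change before any comparison of outcomes by arm. Because patients are unblinded individually at Day 85, no single unblinding date can serve as the deadline.

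The cost is one protocol amendment with three wording edits and one added sentence. It needs no new data, visits or patients. The Week 25 referral screen in Section 6.3 also uses a threshold above 11; that is a clinical rule, which the sponsor should reconcile with the severity table separately, and this change leaves it untouched.

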### Analytical Plan for PHQ-9 Outcome

PHQ-9 outcomes can be summarized into ordinal statistics or dichotomized variables, thus the same analytical procedure for QIDS outcomes can be adapted here. We expect the same statistical power for data analysis using a similar Generalized Linear Model (GLM) framework for depression risk estimation and correlation control using Generalized Estimating Equation (GEE). Therefore, detailed statistical power justification is omitted.

### Equivalence of Results

Analyses using QIDS and PHQ-9 will be conducted separately. The results from them will be compared for equivalence of results purpose. The comparison will include directions of effective size, level of significance of the potential changes, and biological dispersion of estimations from both metrics.

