### **3.1 Study Characteristics**

Patients may be non-depressed or depressed. Those who are severely depressed according to the Quick Inventory of Depression Survey (QIDS  $\geq 16$  points) will be referred to a psychiatrist for further evaluation and possibly additional therapy, based on clinical judgement. The study will be started at University Hospitals Cleveland Medical Center with the possibility that it can be opened at alternative sites if needed for patient accrual.

At the time of study enrollment, the treating physician must have the intent to treat the patient with 12 weeks of neoadjuvant chemotherapy as standard of care cancer treatment. For this study, patients will be randomized in a 1:1 ratio to receive escitalopram or placebo using a randomization table prepared by the study statistician. This randomization table will be shared by the statistician only with the Investigational Drug Services Pharmacy (IDS) personnel and will detail for all 55 patients/study IDs whether that patient is to receive escitalopram or placebo. Each patient will be

assigned a study number, in sequential order, only after all eligibility criteria have been confirmed by the study coordinator, treating physician (Investigator or Co-investigator) involved in the case, and by a member of the Clinical Trials Unit's Quality Assurance department.

It is possible that burden of disease could influence mood. Therefore, patients will also be stratified according to whether they have resectable disease or locally advanced disease (borderline resectable or unresectable) according to NCCN criteria. A pancreatic surgeon (PI or Co-Investigator) will determine this status using the Tumor Profile Assessment (see Appendix VIII). The Tumor Profile Assessment is to be filled out by the PI or by the Co-investigator prior to randomization.

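### The QIDS and PHQ-9 equivalence comparison relies on direction, significance level and an undefined dispersion criterion, which cannot show equivalence; it should be a descriptive consistency check

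*Combined protocol and SAP*

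**What the plan says.** Section 14.2 has three linked parts.

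- **Depression.** QIDS-SR is dichotomized, and the 12-week relative risk comes from a modified Poisson GEE. "This comparison will be performed at the one-sided alpha=0.10 level".
- **Analytical Plan for PHQ-9 Outcome.** PHQ-9 may be ordinal or dichotomized, and "the same analytical procedure for QIDS outcomes can be adapted here". No analysis cut-point is set. On power: "We expect the same statistical power for data analysis using a similar Generalized Linear Model (GLM) framework".
- **Equivalence of Results.** The two analyses are run separately, and their results are then compared with equivalence as the stated purpose: "The comparison will include directions of effective size, level of significance of the potential changes, and biological dispersion of estimations from both metrics". Biological dispersion is not defined. There is no margin, no interval for the difference between the two effects, no joint or paired model, no agreement measure and no decision rule.

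The Study Calendar schedules QIDS-SR and PHQ-9 together at every assessment: Days 1, 8, 22, 36, 50, 64, 78 and 85, and Week 25.

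**The concern.** A comparison of significance levels answers a different question from equivalence. A difference in significance does not show that two effects differ. Two non-significant results do not show that they agree, because a small trial can miss an effect on both scales. Two significant results can still have quite different effect sizes. Agreement in direction is a weak requirement, and the dispersion criterion cannot be applied until it is defined.

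The text also leaves the pairing unused. The same patients complete both scales at the same visits, so agreement can be measured patient by patient.

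The question has some value here. Section 1.2 says that no depression tool has been validated in pancreatic cancer and that depressive symptoms overlap with those of the disease. Whether the two scales classify the same patients as depressed is worth reporting, and the present text would not show it. What is at stake is any statement that the two scales give equivalent results.

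**Working it through.** **Inputs from the documents.** One-sided alpha is 0.10 (Section 14.2). Section 14.3 gives 23 patients per arm, a 40% control rate and this claim: "we have 80% power to detect a difference if the true rate in treatment arm is 13.8% using a one-sided alpha of 0.10". Allocation is 1:1 (Section 3.1). PHQ-9 power is taken as equal to QIDS power (Section 14.2).

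**Input not in the documents.** The correlation between the two scales is an assumption, shown as a range.

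**Step 1: reproduce the stated power.** The unpooled standard error is √(0.40×0.60/23 + 0.138×0.862/23) = 0.125. Then Φ(0.262/0.125 − 1.282) gives 79.3%. Exact binomial enumeration of the pooled z test gives 80.1%. The stated 80% is reproduced.

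**Step 2: discordant significance when the true effects are identical.** Treat the two test statistics as bivariate normal with equal means and correlation ρ. Then P(exactly one significant) = 2 × [power − P(both significant)]. For example, at 80% power and ρ = 0.6, P(both significant) = 0.699, so the result is 2 × (0.800 − 0.699) = 0.202.

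| ρ (assumed) | Only one significant, 80% power | Only one significant, 50% power | Both non-significant, no true effect |
|---|---|---|---|
| 0.6 | 20.2% | 29.5% | 83.9% |
| 0.7 | 17.4% | 25.3% | 84.7% |
| 0.8 | 14.2% | 20.5% | 85.6% |
| 0.9 | 10.0% | 14.4% | 86.9% |
| 0.95 | 7.1% | 10.1% | 87.8% |

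The 50% column is an illustrative scenario in which the true effect is smaller than the design assumes. The last column is the false-agreement case. With no treatment effect, most trials would show matching non-significance, which says nothing about whether the scales agree.

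**Step 3: check by simulation.** Two binary outcomes with the same true rates were simulated with 23 patients per arm and 50,000 trials per setting, each tested by the pooled z test at one-sided 0.10. Here the assumed correlation (0.6 to 0.9) is between the latent scores within a patient. Dichotomizing weakens it, so the test statistics correlate only 0.38 to 0.69.

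| True rates | Significance disagrees | Direction disagrees |
|---|---|---|
| 40% vs 13.8% (design) | 17-25% | 4-5% |
| 40% vs 25% (power about 44%) | 25-36% | 16-22% |
| 40% vs 40% | 10-14% | 24-36% |

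The two methods agree where they overlap: a simulated test-statistic correlation of 0.69 gives 17.4%, and the formula at 0.7 gives 17.4%.

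**Step 4: what a paired comparison could show.** At the design rates, the simulated SD of the difference between the two log relative risks (0.5 added to each count) is 0.52 to 0.71 for latent correlation 0.9 to 0.6. The 80% CI for the ratio of relative risks is then ×/÷ exp(1.282 × 0.52) ≈ 1.9 to ×/÷ exp(1.282 × 0.71) ≈ 2.5. Equivalence could be shown only against a very wide margin.

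**Limit.** Steps 2 to 4 use a simple 12-week comparison, not the planned GEE with baseline adjustment and multiple imputation.

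**The case against.** The strongest reply is that the section contains no decision rule. It says that results will be compared and lists what the comparison includes. It sets no threshold and no consequence. On that view it is a descriptive check under a badly chosen heading. Much of this stands, and it is why the point is minor. The section nevertheless names equivalence as the purpose and significance level as a criterion, and both should go.

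A reader might infer three stronger things that the documents do not support.

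- *That the comparison mostly reflects chance.* At the design effect and 80% power, significance agrees in 80-90% of trials under the stated range of ρ. Direction rarely disagrees at the design effect; it does so often only when the effect is small or absent.
- *That direction and significance are the only criteria.* A third is listed. It may be meant as the spread of the estimates, but without a definition it does not repair the comparison.
- *That the trial's main conclusion is exposed.* The primary analysis uses QIDS alone and the sample size rests on it. Sections 2.1 to 2.4 do not name PHQ-9 as an endpoint.

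It is also fair to object that a formal alternative would be weak. With 23 per arm the paired ratio is imprecise. Kappa addresses patient classification, not whether the treatment effects agree. The scales also have different recall periods, seven days for QIDS (Appendix IV) and two weeks for PHQ-9 (Appendix VII), so some disagreement is expected. These limits stand, and they are a reason to describe agreement without claiming equivalence.

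**Conclusion.** The point holds as a minor correction to a supportive analysis. The comparison as described cannot show that QIDS and PHQ-9 give equivalent results. With identical true effects and 80% power for each scale, significance would be discordant in about 10-20% of trials. That rests on an assumed test-statistic correlation of 0.6-0.9 and on the plan's own assumption of equal power. It falls to about 7% at a correlation of 0.95, and is 17-25% if the 0.6-0.9 range is applied to the latent scores instead. The qualitative conclusion does not depend on the correlation: matching non-significance is not evidence of agreement at any value of it.

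**What to change.** Amend Equivalence of Results and the linked PHQ-9 paragraph in Section 14.2.

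1. Rename the section a descriptive consistency check. Remove the significance-level comparison, the undefined dispersion criterion and any claim of equivalence.
2. Report the QIDS and PHQ-9 relative risks at 12 weeks side by side, each with an 80% CI.
3. Report patient-level percent agreement and kappa, with a CI, between the two moderate-or-worse classifications at the same visit. Note the different recall periods.
4. Fix both cut-points first. Section 2.4 defines QIDS depression as a score of 11 or more, while Sections 12.0, 14.2 and 14.3 require more than 11. One definition must be chosen and used throughout. For this analysis, dichotomize PHQ-9 at 10 or more, where the moderate band begins in Section 1.2.
5. Optionally, add the paired ratio of the two relative risks as a description, stating that its 80% CI would be about ×/÷ 1.9-2.5 with 23 per arm. If it is bootstrapped by patient, say how empty cells are handled. About 3 events are expected in the escitalopram arm (0.138 × 23 = 3.2), and with 3 events about 4% of resamples of that arm contain none ((20/23)^23 = 0.04).

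The cost is a few lines of text and modest extra analysis on data already scheduled; the optional ratio adds more work when combined with multiple imputation. The trial also gives up the option of claiming that the two scales give equivalent results.
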